## 5. TREATMENT OF PATIENTS

### 5.1. Description of Study Drug

Patisiran Solution for Injection is a ribonucleic acid interference (RNAi) therapeutic consisting of an siRNA targeting TTR messenger RNA (mRNA) formulated in a LNP. The patisiran drug product is a sterile formulation of ALN-18328, an siRNA targeting TTR, formulated as LNPs siRNA with lipid excipients (DLin-MC3-DMA, 1,2-Distearoyl-sn-glycero-3-phosphocholine [DSPC], cholesterol, and PEG2000-C-DMG in isotonic phosphate buffered saline. Patisiran Solution for Injection contains 2 mg/mL of the TTR siRNA drug substance.

### 5.2. Concomitant Medications

Use of the following medications/treatments is prohibited during study participation:

- Any investigational agent other than patisiran
- Corticosteroids other than those administered as premedications prior to the dose of patisiran, those used to treat an infusion reaction, or topical or inhaled corticosteroids. However, for patients with chronic inflammatory disorders (eg, asthma, rheumatoid arthritis), systemically administered steroids may be permitted provided that: 1) the dose is <20 mg/day prednisone or equivalent if administered chronically, or 2) for doses ≥20 mg/day, administration is limited to no more than 5 consecutive days.

Use of the medications/treatments listed below is permitted in patients who were already taking such medications while on the parent study in accordance with the rules of that study protocol. For patients who did not take these medications while on the parent study, use of these medications is permitted, if necessary, only after the patient has completed the 52-week visit.

- Tafamidis
- Diflunisal
- Doxycycline/TUDCA

Medications and treatments other than those specified above, including palliative and supportive care approved by the Investigator for disease-related symptoms, are permitted during the study.

All patients will be asked to continue to take an oral daily supplement containing the recommended daily allowance of vitamin A.

Any concomitant medication or treatment that is required for the patient's welfare may be given by the Investigator. Use of all concomitant medications and treatments will be recorded on the patient's CRF through the end of the patient's participation in the study. This will include all prescription drugs, herbal preparations, over-the-counter (OTC) medications, vitamins, and minerals. Any changes in medications during the study will also be recorded on the CRF. Similarly, concomitant medications that continue from the parent study will be entered into the database.

### **5.3. Treatment Compliance**

Compliance with patisiran administration is dependent on the proper preparation and administration of IV infusions by trained personnel and attendance by the patient at the clinic for scheduled assessment visits. Compliance with patisiran administration will be verified through observation by study staff. A dose will be considered completed if 80% or more of the total volume of the IV solution was administered to the patient. Patients will be permitted to miss an occasional dose of patisiran; however, if a patient misses 3 consecutive doses, the Investigator, in consultation with the Medical Monitor, will discuss whether the patient will be able to continue on the study.

### **5.4. Randomization and Blinding**

This is an open-label study; however, patients rolling over into this study from a previously blinded study will remain blind to their previous treatment assignment until database lock has occurred in that study.

## 6. STUDY DRUG MATERIALS AND MANAGEMENT

### 6.1. Study Drug Packaging and Labeling

All packaging, labeling, and the preparation of patisiran will be in compliance with Good Manufacturing Practice (GMP) specifications, as described in the Manufacture of Investigational Medicinal Products Volume 4 Annex 13, and any other or local applicable regulations.

Patisiran labels will include all appropriate local labeling requirements on the vial and external label. Sample labels will be submitted to health authorities, per local country submission requirements.

The patisiran drug product is packaged in 10 mL glass vials with a fill volume of 5.5 mL. The container closure system consists of a United States Pharmacopeia/European Pharmacopoeia (USP/EP) Type I borosilicate glass vial, a Teflon-faced butyl rubber stopper, and an aluminium flip-off cap.

### 6.2. Study Drug Storage

Patisiran will be stored upright and refrigerated at approximately  $5 \pm 3^{\circ}\text{C}$ . Any deviation from the recommended storage conditions must be reported to the CRO and/or the Sponsor and use of the patisiran halted until authorization for its continued use has been given by the Sponsor or designee.

No special procedures for the safe handling of patisiran are required. A Sponsor representative or designee will be permitted, upon request, to audit the supplies, storage, dispensing procedures, and records.

Patisiran supplied for this study may not be administered to any person not enrolled in the study.

### 6.3. Study Drug Preparation

Staff at each clinical site or the healthcare professional administering patisiran will be responsible for preparation of patisiran doses, according to procedures detailed in the Pharmacy Manual.

All patients in this study will receive 0.3 mg/kg patisiran once every 21 days ( $\pm 3$  days). The amount (mg) of patisiran to be administered will be based on the patient's body weight (kg). For each dose administered, the weight obtained during the previous dosing visit will be used to calculate the dose of patisiran. In the event that the weight obtained on the previous dosing day is not available, the weight obtained pre-dose on the current dosing day can be used for dose calculation. Patients who weigh 105 kg or more will receive patisiran dosing based on an assumption of a body weight of 104 kg.

Patisiran will be prepared under aseptic conditions. The total amount to be infused into each patient at each dosing visit will be 200 mL. Sterile normal saline (0.9% NaCl) will be added to a sterile infusion bag, and the calculated volume of patisiran will be withdrawn from the vials and injected into the infusion bag.

## 6.4. Administration

### 6.4.1. Premedication

Prior to each dose of patisiran, patients will receive the following premedications in order to reduce the risk of experiencing an IRR at least 60 minutes before the infusion:

- Intravenous dexamethasone (10 mg) or equivalent
- Oral paracetamol/acetaminophen (500 mg) or equivalent
- Intravenous H2 blocker (ranitidine 50 mg, famotidine 20 mg, or equivalent other H2 blocker dose)
- Intravenous H1 blocker: diphenhydramine 50 mg (or equivalent other IV H1 blocker available at the clinical site). Hydroxyzine 25 mg per os (PO, orally) or fexofenadine 30 mg or 60 mg PO or cetirizine 10 mg PO may be substituted for any patient who does not tolerate IV diphenhydramine or other IV H1 blocker.

Further details (including a table of equivalent premedications) can be found in the patisiran Pharmacy Manual.

Patients will be started on the above premedication regimen. However, modifications may be made to the premedication regimen after consultation with the medical monitor either due to a patient's inability to tolerate one or more of the premedications or to the occurrence of IRRs unresponsive to slowing of the infusion rate.

- If a patient is having difficulty tolerating the steroid premedication regimen (e.g., patient develops uncontrolled hyperglycemia, altered mental status, or other complication), then lowering of the steroid premedication may be allowed for that patient after consultation with the medical monitor.
- If after consultation with the medical monitor, it is agreed that an individual patient's steroid premedication will be lowered, then the following steps **must be followed**:
  - 1) If the current steroid dosage is 10 mg or less of intravenous dexamethasone or equivalent, then the patient may be lowered in increments no greater than 2.5 mg intravenous dexamethasone or equivalent.
  - 2) After each incremental lowering of intravenous dexamethasone or equivalent, the patient must receive three consecutive intravenous doses of patisiran without IRR and continued signs or symptoms of steroid intolerance before further reductions in steroid premedications.
  - 3) The premedication steroid dosage should not be reduced below 5 mg intravenous dexamethasone or equivalent.

Alternatively if a patient experiences an IRR when 10 mg or less of IV dexamethasone or equivalent is used as the steroid premedication, then proceed to Section 6.4.3.

If a patient's premedication regimen was modified prior to enrollment in Study TTR02-006, the patient may continue on that modified premedication regimen.

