## 6.4. Administration

### 6.4.1. Premedication

Prior to each dose of patisiran, patients will receive the following premedications in order to reduce the risk of experiencing an IRR at least 60 minutes before the infusion:

- Intravenous dexamethasone (10 mg) or equivalent
- Oral paracetamol/acetaminophen (500 mg) or equivalent
- Intravenous H2 blocker (ranitidine 50 mg, famotidine 20 mg, or equivalent other H2 blocker dose)
- Intravenous H1 blocker: diphenhydramine 50 mg (or equivalent other IV H1 blocker available at the clinical site). Hydroxyzine or fexofenadine 25 mg per os (PO, orally) or cetirizine 10 mg PO may be substituted for any patient who does not tolerate IV diphenhydramine or other IV H1 blocker.

Further details (including a table of equivalent premedications) can be found in the patisiran Pharmacy Manual.

Patients will be started on the above premedication regimen. However, modifications may be made to the premedication regimen after consultation with the medical monitor either due to a patient's inability to tolerate one or more of the premedications or to the occurrence of IRRs unresponsive to slowing of the infusion rate.

- If a patient is having difficulty tolerating the steroid premedication regimen (e.g., patient develops uncontrolled hyperglycemia, altered mental status, or other complication), then lowering of the steroid premedication may be allowed for that patient after consultation with the medical monitor.
- If after consultation with the medical monitor, it is agreed that an individual patient's steroid premedication will be lowered, then the following steps **must be followed**:
  - 1) If the current steroid dosage is 10 mg or less of intravenous dexamethasone or equivalent, then the patient may be lowered in increments no greater than 2.5 mg intravenous dexamethasone or equivalent.
  - 2) After each incremental lowering of intravenous dexamethasone or equivalent, the patient must receive three consecutive intravenous doses of patisiran without IRR and continued signs or symptoms of steroid intolerance before further reductions in steroid premedications.
  - 3) The premedication steroid dosage should not be reduced below 5 mg intravenous dexamethasone or equivalent.

Alternatively if a patient experiences an IRR when 10 mg or less of IV dexamethasone or equivalent is used as the steroid premedication, then proceed to Section [6.4.3](#).

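### Step 2 of the mandatory steroid-lowering rule (Protocol 6.4.1), read on its plain grammar, bars a second reduction for the still-intolerant patient whom lowering is meant to help

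*Protocol*

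**What the plan says.** Section 6.4.1 (Premedication, Version 3.1 Brazil) starts every patient on 10 mg intravenous dexamethasone or equivalent. The reason for lowering it is stated: "If a patient is having difficulty tolerating the steroid premedication regimen", with uncontrolled hyperglycemia and altered mental status among the examples. The medical monitor must be consulted first. Once "it is agreed that an individual patient's steroid premedication will be lowered, then the following steps" are marked, in bold, as mandatory:

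- Step 1, for a current dose of 10 mg or less: "the patient may be lowered in increments no greater than 2.5 mg intravenous dexamethasone or equivalent".
- Step 2, between cuts: "the patient must receive three consecutive intravenous doses of patisiran without IRR and continued signs or symptoms of steroid intolerance before further reductions".
- Step 3: "The premedication steroid dosage should not be reduced below 5 mg intravenous dexamethasone or equivalent".

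The step 2 sentence also stands in Section 6.4.1 of Version 2.1 Brazil and of Version 2.1 France and Germany: "without IRR and continued signs or symptoms of steroid intolerance before further reductions in steroid premedications".

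**The concern.** Step 2 can be read in two ways.

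- Reading A: *without* applies to both nouns, so a further cut needs three doses with no IRR and no continuing intolerance. This is what the words most directly say.
- Reading B: three doses with no IRR, while intolerance continues. This fits the purpose of lowering but needs a *with* that is not written.

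Reading A works against the reason for the rule. The patient still troubled by the steroid at 7.5 mg is the one with grounds for a second cut, and A refuses it. The steps are binding, so a site that follows the text literally would hold that patient above the dose that step 3 permits. What is at stake is steroid exposure and tolerability for individual patients. No efficacy or IRR analysis changes.

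**Working it through.** No figure in the plan needs reproducing. The check is a reading of the clauses together, plus short arithmetic.

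**Inputs.** Starting dose 10 mg, maximum cut 2.5 mg, floor 5 mg and wait of three doses (all Section 6.4.1); dosing interval 21 (±3) days (Section 6.4.2).

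**Where step 2 applies.** Cuts needed from 10 mg to the floor, at the maximum size: (10 − 5) / 2.5 = 2, that is 10 → 7.5 → 5 mg. The first cut has no preceding cut, so step 2 governs one decision, 7.5 → 5 mg. From 7.5 mg the number is (7.5 − 5) / 2.5 = 1, so a patient who enters on 7.5 mg can reach 5 mg without step 2. Step 1 also allows smaller cuts, in which case step 2 applies more often.

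**What each reading gives at 7.5 mg.** Step 2 is a condition that must be met before a cut. It does not by itself authorise one; the ground for lowering is the intolerance named earlier in the section. Taking both together:

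| Over the three doses | Reading A | Reading B |
|---|---|---|
| Any IRR | no cut | no cut |
| No IRR, still intolerant | no cut | 5 mg allowed |
| No IRR, no longer intolerant | wait met, but no stated ground for a cut | no cut |

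The readings lead to different doses only in the middle row. On A, no row ends in a permitted cut; the only case left is a patient whose intolerance returns after three clear doses. B gives every clause something to do, which is why it is the likely intent.

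**Size for the middle row.** On B the wait is 3 × 21 = 63 days, or 3 × 18 = 54 to 3 × 24 = 72 days at the limits of the dosing window. On A the patient stays at 7.5 mg while intolerance lasts: 7.5 − 5 = 2.5 mg more per infusion.

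**Does other text settle it?** Section 6.4.3 deals with raising the steroid after an IRR, and its steps are only recommended. The last paragraph of 6.4.1 covers regimens changed before enrolment ("the patient may continue on that modified premedication regimen"). Section 5.2 allows treatment of the complication ("Any concomitant medication or treatment that is required for the patient's welfare may be given by the Investigator") but does not say how step 2 is to be applied. None of these resolves the wording.

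**The case against.** The best reply is that nobody would apply reading A in practice. The section ties lowering to intolerance, so context points to B. The medical monitor must be consulted before the steroid is lowered and would know the purpose. Section 6.4.1 also refers to a Pharmacy Manual, which is not available here and may explain tapering. Most of this stands, and it is why the effect is small. It does not repair the sentence: the steps are binding once lowering is agreed, and no text at hand lets the monitor set step 2 aside.

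A reader might also infer that A does harm in the other direction, by letting a patient who has recovered be cut further and lose IRR protection for nothing, so that the readings give opposite answers for two kinds of patient. The documents do not support that. Meeting the step 2 wait is not a reason to lower, and a patient who now tolerates the steroid has no stated ground for another cut on either reading.

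**Conclusion.** The sentence is wrong as written. Its plain grammar refuses a second reduction to the IRR-free patient who is still intolerant, against the stated reason for lowering and the 5 mg floor. The consequence is confined to that patient: 5 mg after about 63 days (54 to 72), or 7.5 mg for as long as intolerance continues. This assumes cuts of the maximum 2.5 mg from 10 mg, and a site and medical monitor who take the words literally. The documents do not say how many patients are affected, and treatment of the complication remains available. It is a small point about a mandatory safety instruction, worth correcting because the correction is so cheap. That *without* governs both nouns is a judgement about grammar, though the natural one.

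**What to change.** Reword step 2 of Section 6.4.1: *After each incremental lowering, the patient must receive three consecutive doses of patisiran without an IRR; if signs or symptoms of steroid intolerance continue, a further reduction may then be made.* Steps 1 and 3 stay as they are. Any other country version still in use with the same sentence should get the same change. The cost is one sentence at the next amendment or in a clarification letter, a route already used in this study for the timing of pregnancy tests (Version 3.1 Argentina summary of changes). No new procedures or data are needed.

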subjects of Japanese origin (Study ALN-TTR02-005) also showed dose dependent reduction in serum TTR, similar to that observed in Study ALN-TTR02-001 in Caucasian subjects; patisiran was safe and well tolerated up to 0.3 mg/kg. An open-label Phase 2 multiple ascending dose study of patisiran in ATTR patients with FAP (Study ALN-TTR02-002) was conducted to determine the safety and tolerability, PK, and pharmacodynamics (PD) of a 60 or 70 minute IV infusion of patisiran administered once every 3 or 4 weeks for 2 doses. The top dose of 0.3 mg/kg administered every 3 or 4 weeks was found to be generally safe and well tolerated, with maximum TTR knockdown of ~90% and sustained TTR suppression of >80% most consistently observed with every 3 week dosing. Twenty seven of the 29 patients treated on the Phase 2 trial enrolled in an open-label extension study (ALN-TTR02-003) to evaluate safety and tolerability of long-term dosing with patisiran for approximately 2 years. Multiple doses of patisiran have been generally safe and well-tolerated on the -003 study, with preliminary data indicating no changes in liver function tests, renal function, or hematologic parameters, and no treatment-related discontinuations. Sustained suppression of serum TTR of >80% has been observed in the open-label extension study, and preliminary clinical data at 6 months showed evidence for disease stabilization. A randomized, double-blind, placebo-controlled Phase 3 study of patisiran (ALN-TTR02-004; APOLLO) is ongoing worldwide. The main objectives of the study are to demonstrate the clinical efficacy of patisiran and to establish the safety of chronic dosing in ATTR patients with FAP. Further details on the clinical studies of patisiran can be found in the patisiran Investigator's Brochure.

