### 1.3. Study Design Rationale

This is a multicenter, open-label extension study designed to evaluate the long-term safety and efficacy of patisiran in patients with FAP who have completed a prior study with patisiran.

The nonclinical data and clinical experience with patisiran support the continuation of patisiran treatment in this long-term extension study for ATTR patients with FAP. All patients will receive patisiran at 0.3 mg/kg administered IV every 3 weeks, which is the dose and regimen employed in the ongoing Phase 3 study with patisiran. Various clinical evaluations will be performed periodically as outlined in [Table 1](#) to continue to assess the effect of patisiran beyond the duration of the ongoing clinical studies, and will enable all patients who have completed a prior study with patisiran (provided they meet the eligibility criteria of this study), including those previously on placebo, to receive open-label patisiran. Patients coming on to this open-label study from a blinded study will remain blinded to their previous treatment assignment until at least database lock has occurred in that study. The duration of the study has been determined to allow the collection of long-term safety, tolerability and efficacy data of patisiran in patients with FAP who have completed a prior study with patisiran. The estimated duration of the study is 5 years.

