## 4. SELECTION AND WITHDRAWAL OF PATIENTS

### 4.1. Patient Inclusion Criteria

To be enrolled in the study, patients must meet the following criteria before administration of patisiran on Day 0:

1. Have completed a patisiran study (ie, completed the last efficacy visit in the parent study) and, in the opinion of the investigator, tolerated study drug
2. Be considered fit for the study by the Investigator
3. Have aspartate transaminase (AST) and alanine transaminase (ALT) levels  $\leq 2.5 \times$  the upper limit of normal (ULN), international normalized ratio (INR)  $\leq 2.0$  (patients on anticoagulant therapy with an INR of  $\leq 3.5$  will be allowed)
4. Have a total bilirubin within normal limits. A patient with total bilirubin  $\leq 2 \times$  ULN is eligible if the elevation is secondary to documented Gilbert's syndrome (elevation of unconjugated bilirubin with normal conjugated bilirubin) and the patient has ALT and AST levels within normal ranges.
5. Have a serum creatinine  $\leq 2 \times$  ULN
6. Women of child-bearing potential must have a negative pregnancy test, cannot be breastfeeding, and must be using 2 highly effective methods of contraception prior to dosing in this study and agree to use 2 highly effective methods of contraception throughout study participation and for 75 days after last dose of patisiran in this study. Highly effective methods of birth control are defined in Section 4.4.
7. Males with partners of child-bearing potential must agree to use 1 barrier method (eg, condom) and 1 additional method (eg, spermicide) of contraception throughout study participation and for 75 days after the last dose of patisiran in this study; males must also abstain from sperm donation after the first dose of patisiran through study participation and for 75 days after last dose of patisiran in this study
8. Be willing and able to comply with the protocol-required visit schedule and visit requirements and provide written informed consent

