### 4.2. Patient Exclusion Criteria

A patient will be excluded if they meet any of the following criteria before dosing on Day 0:

1. Has an active infection requiring systemic antiviral or antimicrobial therapy that will not be completed before the first dose of patisiran administration
2. Has poorly controlled diabetes mellitus
3. Has uncontrolled cardiac arrhythmia or unstable angina
4. Is currently taking tafamidis, diflunisal, doxycycline, or tauroursodeoxycholic acid (TUDCA), unless previously allowed per the parent study

5. Is unable to take the required premedications, unless modifications to the premedication regimen were previously allowed per the parent study
6. Is under legal protection (defined as “any person who becomes incapable of protecting his/her interests due to a medically diagnosed impairment of his/her mental faculties that may limit or prevent the expression of his will”), decided by a court

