**Rationale for Version 2.1-Brazil**

Consistent with Brazil-specific protocol ALN-TTR02-004, pregnancy testing for women of child-bearing potential prior to each dose of patisiran has been included in Brazil-specific protocol ALN-TTR02-006.

A detailed summary of changes is provided in [Table 1](#). Corrections to typographical errors, punctuation, grammar, abbreviations, and formatting are not detailed.

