5. Is unable to take the required premedications, unless modifications to the premedication regimen were previously allowed per the APOLLO study
6. Is under legal protection (defined as "any person who becomes incapable of protecting his/her interests due to a medically diagnosed impairment of his/her mental faculties that may limit or prevent the expression of his will"), decided by a court

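### The premedication carry-over sentence in 6.4.1 ignores prior patisiran exposure: if the blinded parent study allowed steroid lowering, a former placebo patient could take the first patisiran infusion on reduced dexamethasone without a Medical Monitor consultation in this study

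*Protocol*

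**What the plan says.** All of this is in the Protocol, Version 3.1 Brazil, unless another version is named.

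- **Default and lowering rule (6.4.1).** Patients start on 10 mg IV dexamethasone or equivalent plus the other premedications. Modifications follow consultation with the Medical Monitor. Steroid lowering goes in steps of at most 2.5 mg, needs three IRR-free patisiran infusions in a row before a further step, and should stop at 5 mg.
- **Carry-over (end of 6.4.1).** "If a patient's premedication regimen was modified prior to enrollment in Study TTR02-006, the patient may continue on that modified premedication regimen". The sentence names no parent-study arm, no prior patisiran exposure and no consultation. Version 2.1 Brazil and Version 2.1 France and Germany carry the same sentence. They are earlier texts and add no independent support.
- **Eligibility (4.2, exclusion 5).** A patient who cannot take the required premedications is excluded, "unless modifications to the premedication regimen were previously allowed per the parent study". The Japan version (2.2) words the same exception as "unless modifications to the premedication regimen were previously allowed per the APOLLO study".
- **Who enrols (1.2, 1.3, 5.4).** The parent studies include a blinded one: "A randomized, double-blind, placebo-controlled Phase 3 study of patisiran (ALN-TTR02-004; APOLLO) is ongoing worldwide". The extension enables all eligible completers, "including those previously on placebo, to receive open-label patisiran". Patients from a blinded study stay blinded to their earlier assignment until that study's database lock.

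**The concern.** In this study the safety condition for reducing the steroid further is tolerance of patisiran itself. A patient who had placebo in the parent study has no such record. Inclusion criterion 1 asks that the patient, "in the opinion of the investigator, tolerated study drug", but for this patient the study drug was placebo, so the criterion says nothing about tolerating patisiran on less steroid.

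The carry-over sentence does not separate this patient from one who has had patisiran before. Premedication is given to reduce the risk of infusion-related reactions. A patient new to patisiran could therefore begin with less steroid cover than the protocol's own ladder would allow at that point, and nothing in the text prompts a Medical Monitor consultation first.

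**Working it through.** No sample size, power or error rate is involved. The check compares two routes to a reduced steroid dose and then looks for text that would close the gap.

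**Inputs (6.4.1, 6.4.2).** Standard dose 10 mg; largest step 2.5 mg; 3 IRR-free patisiran infusions before a further step; in-study floor 5 mg; dosing every 21 days, window ±3 days.

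**Size of the reduction**
- 7.5 mg: (10 − 7.5) / 10 = 25% less dexamethasone.
- 5 mg: (10 − 5) / 10 = 50% less.

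**Route 1: lowering within this study, fastest case**

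| Infusion | Dexamethasone | Patisiran infusions already given |
|---|---|---|
| 1 | 10 mg | 0 |
| 2, 3, 4 | 7.5 mg | 1, 2, 3 |
| 5 | 5 mg | 4 |

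Infusion 5 falls nominally on Day 4 × 21 = 84. If the window is taken to apply to each interval (an assumption), the range is 4 × 18 = Day 72 to 4 × 24 = Day 96. Each lowering follows a Medical Monitor consultation.

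**Route 2: carry-over by a former placebo patient.** Either 7.5 or 5 mg is possible at infusion 1 (Day 0), after 0 patisiran infusions. Consultation in 6.4.1 attaches to making a modification, so continuing an existing one does not trigger it in this study.

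**Does other text close the gap?**
- The default start at 10 mg does not, because the carry-over sentence is the specific exception to it.
- Exclusion 5 does not. It accepts modifications allowed in the parent study without regard to arm.
- Sections 6.4.2 and 6.4.3 deal with the infusion and with reactions. They do not set the starting steroid dose.
- The carry-over rule for infusion time in 6.4.2 makes a useful contrast. It keeps a more cautious setting (a longer infusion), and a return to 70 minutes needs a Medical Monitor discussion. The premedication rule can keep a less cautious setting with no discussion.

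**Who could be affected?** Section 1.2 reports 27 patients enrolled in the open-label study ALN-TTR02-003. Any roll-overs from there have already had patisiran and are outside the concern. That leaves an unknown subset, possibly empty, of the roll-overs from ALN-TTR02-004.

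**The case against.** The strongest objection is that the scenario depends on a document not at hand. The parent protocol would have to allow steroid lowering, a placebo patient would have to have been lowered, and that patient would have to roll over. Exclusion 5 does not establish any of this. It is a conditional clause, and a premedication modification can also be an increase after a reaction or a change to a non-steroid drug. The Japan wording is the same criterion with the study named, so it is not a second source. The Brazil rationale "Consistent with Brazil-specific protocol ALN-TTR02-004" shows that a Brazil-specific parent protocol existed, but it concerns pregnancy testing. This objection stands in full and is why the point is conditional.

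The gap is also small. The protocol accepts 7.5 mg after a single patisiran infusion and 5 mg as a floor, so for a 7.5 mg carry-over the two routes differ by one infusion. A consultation may also have taken place in the parent study. Both points are fair. Neither supplies a consultation here before the first patisiran infusion.

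A reader might infer three stronger claims that the documents do not support:

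- **That nobody in this study weighs the risk.** Continuing the regimen is optional, and inclusion criterion 2 requires the Investigator to judge the patient fit. What is missing is a Medical Monitor consultation, not clinical judgment.
- **That a reaction on a reduced dose goes unmanaged.** The last part of 6.4.1 sends an IRR on 10 mg or less to 6.4.3, and a severe IRR stops dosing until the Medical Monitor has discussed the case.
- **That step 3 of the steroid-increase guidance in 6.4.3 also needs rewriting.** For a former placebo patient carried over at 5 mg, the earlier IRR-free dose could be 7.5 mg, established only on placebo. But 6.4.3 already places a steroid increase behind Medical Monitor consultation, and its steps are only recommended. Accepting an earlier dose only when active assignment is known would also discard, before unblinding, the valid records of patients who really had patisiran.

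**Conclusion.** The point holds as a cheap, conditional improvement to patient safety, with low confidence. The carry-over sentence is consistent with exclusion 5, and calling it a contradiction or a demonstrated error would go too far.

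What the text does permit is a first patisiran infusion on 7.5 or 5 mg dexamethasone in a patient with no patisiran exposure, where the in-study ladder would require at least 1 or 4 earlier patisiran infusions and a consultation at each lowering. This rests on the assumption that the blinded parent study allowed steroid lowering and that a placebo patient was lowered and enrolled here.

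The documents give neither the number of such patients nor an IRR rate by steroid dose, so the added risk cannot be stated. The other premedications, the stepwise infusion and the hour on site after each of the first 3 infusions limit it further.

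**What to change.** After the carry-over sentence in 6.4.1 of Version 3.1 Brazil, and of any other current version that carries it, add:

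> *A patient from a blinded parent study whose prior assignment is unknown or was placebo, and who enters on less than 10 mg IV dexamethasone or equivalent, receives the first patisiran infusion of this study on that dose only after consultation with the Medical Monitor, weighing IRR risk against the documented steroid intolerance.*

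The wording works while assignment is still blinded and leaves patients known to have had active drug as they are. Section 6.4.3 can stay unchanged.

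The cost is one sentence at the next amendment and one consultation per affected patient before Day 0. Before parent database lock, that includes blinded patients who in fact had patisiran. The downside is that a patient lowered for steroid intolerance, for example uncontrolled hyperglycemia, may be exposed to more steroid again. The sentence leaves that to a case-by-case decision and forces no return to 10 mg.
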